#### 7.1.9 Contouring and Target Definition (please refer to diagram below)

1. Co-registration with CT scans, MRI scans, and PET scans will be used in identifying the CTV volumes
2. The doses prescribed will be based on the boolean(combined) volume of CTV defined by the PET( $T/N \geq 2.0$ ) and the MRI areas of contrast enhancement including the surgical cavity.
  - a. For patients with a combined volume  $\leq 65$  cc, over five treatment days, patients will receive 35 Gy to CTV3500\_PET, 30 Gy to CTV3000\_MR and 25 Gy(CTV2500) to boolean(combined) volume of CTV3500\_PET+CTV3000\_MR+1cm.
  - b. For patients with a combined volume  $> 65$  cc, over ten treatment days, patients will receive 40 Gy to CTV4000\_PET, 35 Gy to CTV3500\_MR and 30 Gy(CTV3000) to boolean(combined) volume of CTV4000\_PET+CTV3500\_MR+1cm.
3. The optimization target volume (OTV) is defined as a margin of 2 mm isotropic expansion of the CTV and edited clinically based on patterns of tumor spreading and anatomic boundaries such as skulls and nasal cavity.
4. All normal structures will be contoured on the standard of each institution.

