## 7.0 Protocol Treatment

### 7.1 Radiation Therapy

**Doses throughout will be prescribed in Gy(RBE)/Gy or Gy. One Gy will be the equivalent of one Gy (RBE)/Gy for proton therapy for the purposes of the descriptions below. Radiation therapy must begin within 8 weeks of the biopsy or surgical resection. The dose and fractionation will be dependent on the combined volume of the CTV of the PET(T/N>2.0) and MRI (T1 cavity+T1 contrast enhancement)-see section 7.1.9. Radiation will be delivered one fraction/day on consecutive days excluding weekends.**

- 7.1.1 Immobilization and CT simulation: performed based on the standard of each institution.
- 7.1.2 Treatment planning utilizing image fusion with F-Dopa-PET and MRI imaging. Currently, F-DOPA is an investigational diagnostic PET radiopharmaceutical. Investigational new drug (IND) application of F-DOPA will be submitted to FDA by Nuclear Medicine of Department of Radiology. The on-site cyclotron facilities will be able to produce F-DOPA PET tracer for this clinical research project.

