#### Five Fraction Regimen ( $\leq 65\text{cc}$ )

$\text{CTV3500\_PET} = \text{PET T/N} \geq 2.0$   
 $\text{CTV3000\_MR} = \text{Boolean}(\text{T1\_Gad} + \text{T1\_Cavity})$   
 $\text{Boolean CTV3500\_PET} - \text{CTV3000\_MR} \leq 65\text{cc}$   
 $\text{CTV2500} = (\text{Boolean CTV3500\_PET} + \text{CTV3000\_MR}) + 1\text{cm}$

Optimization Target Volume (OTV)  $\geq 2\text{mm} + \text{CTV2500}$

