#### Ten Fraction Regimen ( $> 65\text{cc}$ )

$\text{CTV4000\_PET} = \text{PET T/N} > 2.0$   
 $\text{CTV3500\_MR} = \text{Boolean}(\text{T1\_Gad} + \text{T1\_Cavity})$   
 $\text{Boolean CTV4000\_PET} - \text{CTV3500\_MR} > 65\text{cc}$   
 $\text{CTV3000} = (\text{Boolean CTV3500\_PET} + \text{CTV3000\_MR}) + 1\text{cm}$

Optimization Target Volume (OTV)  $\geq 2\text{mm} + \text{CTV3000}$

\*Need to make sure all CTVs are inside the brain tissue contour

\*Need to evaluate inclusion or exclusion of small CTV volumes at a considerable distance from bulk CTV volumes

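### The 65 cc test that selects five or ten fractions is the combined PET and MRI volume in the text but is printed with a minus or dash in both regimen boxes; the ten-fraction box also carries five-fraction volume names

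*Combined protocol and SAP*

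**What the plan says.** Three places in the protocol bear on how a patient is assigned to a regimen.

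- Section 7.1 (Radiation Therapy): "The dose and fractionation will be dependent on the combined volume of the CTV of the PET(T/N>2.0) and MRI (T1 cavity+T1 contrast enhancement".
- Section 7.1.9, item 2: "The doses prescribed will be based on the boolean(combined) volume of CTV", as defined by PET and by the enhancing MRI areas with the surgical cavity. Items 2a and 2b then set five treatment days for a combined volume of at most 65 cc and ten treatment days above it.
- The two regimen boxes, to which the heading of 7.1.9 sends the reader. The five-fraction box gives the test as "Boolean CTV3500\_PET} - \text{CTV3000\_MR} \leq 65\text{cc" and the ten-fraction box as "Boolean CTV4000\_PET} - \text{CTV3500\_MR} > 65\text{cc". The typesetting code is as read from the file. Each line shows the PET volume, a minus or dash, the MR volume, and then the comparison with 65 cc.

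On the low-dose target of the ten-fraction regimen, item 2b prescribes "30 Gy(CTV3000) to boolean(combined) volume of CTV4000\_PET+CTV3500\_MR+1cm". The ten-fraction box instead gives "CTV3000} = (\text{Boolean CTV3500\_PET} + \text{CTV3000\_MR}) + 1\text{cm".

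**The concern.** The 65 cc comparison decides each patient's regimen. More follows from it than the number of treatment days: the three prescribed dose levels (items 2a and 2b of 7.1.9), the critical-structure limits (Table 7.1 has separate five- and ten-fraction panels), and the days of concurrent temozolomide (7.3: days 1-7 or days 1-14).

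Boolean addition and Boolean subtraction are both ordinary contouring operations, so a line that starts with Boolean and puts a minus between two structures can be read as an instruction to subtract. A planner working from the box could then choose a different regimen from one working from the text. Patients are planned at two sites (3.1.3), so the two readings could coexist in the trial. The primary analysis in Section 16 makes no distinction by regimen, so the decision rule itself would not change. What would be less well defined is the treatment that the result describes.

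The volume names in the ten-fraction box raise a second, smaller question: whether CTV3000 would be built from structures that do not belong to that regimen.

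**Working it through.** The protocol states no figure to reproduce here. The check is a comparison of the printed rules, followed by set arithmetic.

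**Step 1: do the two readings define the same volume?** Write P for the PET volume, M for the MR volume and O for their overlap, all in cc.

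- Combined volume (7.1 and 7.1.9): U = P + M − O.
- Box line read as Boolean subtraction: D = P − O.
- Gap: U − D = M.

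The two differ by the whole MR volume. Since M is never negative, D never exceeds U. If the line is instead read as plain subtraction of two volumes, P − M, the result is no larger than D, because O cannot exceed M. Either way the direction is the same.

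**Step 2: when does the assignment differ?** It differs when U > 65 and U − M ≤ 65, that is, when 65 < U ≤ 65 + M. The text then gives ten fractions and the box gives five. The reverse cannot happen.

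**Step 3: illustrations.** The documents give no volumes, so all of these are assumed.

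| P | M | O | Combined U | Difference D | By the text | By the box, if subtraction |
|---|---|---|---|---|---|---|
| 40 | 50 | 20 | 40 + 50 − 20 = 70 | 40 − 20 = 20 | ten | five |
| 20 | 80 | 20 | 20 + 80 − 20 = 80 | 20 − 20 = 0 | ten | five |
| 100 | 40 | 30 | 100 + 40 − 30 = 110 | 100 − 30 = 70 | ten | ten |
| 30 | 30 | 10 | 30 + 30 − 10 = 50 | 30 − 10 = 20 | five | five |

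The two readings can agree or disagree depending on the anatomy. Without a distribution of P, M and O, the proportion of patients affected cannot be calculated.

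**Step 4: the volume names in the ten-fraction box.**

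| Structure | Five-fraction box | Ten-fraction box |
|---|---|---|
| PET volume | `CTV3500_PET`: T/N ≥ 2.0 | `CTV4000_PET`: T/N > 2.0 |
| MR volume | `CTV3000_MR`: Boolean of T1_Gad and T1_Cavity | `CTV3500_MR`: Boolean of T1_Gad and T1_Cavity |
| Expanded target | `CTV2500` = (`CTV3500_PET` + `CTV3000_MR`) + 1 cm | `CTV3000` = (`CTV3500_PET` + `CTV3000_MR`) + 1 cm |

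The right-hand sides in the last row are identical, and the ten-fraction box does not define the two names it uses there. This looks like text carried over from the five-fraction box. But the PET structure is the T/N 2.0 region in both boxes (apart from ≥ against >), and the MR structure is the same Boolean in both. Matching PET to PET and MR to MR therefore gives essentially the same CTV3000 contour under either set of names.

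**The case against.** The strongest reply is that the prose is consistent and the disputed mark is one small symbol. The combined volume is the selector in 7.1 and in items 2, 2a and 2b of 7.1.9, and 16.4.1 also describes combining the two contours and then expanding them. No sentence anywhere describes subtraction. The disputed line begins with Boolean, the word that 7.1.9 glosses as combined. The boxes come from a diagram read by a program, and other small symbols nearby may have suffered: the tracer activity, for instance, appears as 5.0 + 10% mCi. Two boxes built on one template would repeat a joining dash just as they would repeat a minus. All plans are also reviewed (7.1.14), and a physicist co-chair reviews robustness for every patient (7.1.11).

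Most of this stands, and it limits the point. A reader might infer that the boxes direct subtraction and that patients will be misassigned. The documents do not support that: the symbol may be a dash, the text points the other way, and no volumes are given. A reader might also infer from the ten-fraction box that the low-dose target would be built from the wrong structures. The boxes' own definitions do not support that either.

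Two things remain. In both boxes a plus sign is printed on the lines before and after the disputed one, so the boxes use different symbols where the text describes one operation. And the review in 7.1.14 rates deviations in target dose and critical-structure limits, as listed under Prescription Deviations and Goals. No deviation is defined there for choosing the regimen on the wrong volume, so the review need not catch it.

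**Conclusion.** The point holds as a drafting inconsistency in an operative rule, not as a fault in the design. The text defines the 65 cc volume as the combined PET and MRI volume, while both boxes print a symbol that, taken literally, defines a different one. If it were followed as subtraction, any discrepancy would run one way: five fractions by the box where the text gives ten, for combined volumes above 65 cc and up to 65 cc plus the MR volume. That consequence depends on the mark being a true minus and on a planner following it against the text. Neither is established, and the number of patients affected is unknown.

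The wrong volume names in the ten-fraction box are a definite error that does not depend on the symbol. They have essentially no effect on the contour, so this part is a labelling correction only.

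This review takes no view on which volume should select the regimen.

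**What to change.** Reconcile 7.1, 7.1.9 and both regimen boxes so that:

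1. one unambiguous operation, named in words (union or subtraction) and written with the same symbol throughout, defines the volume compared with 65 cc, with the sponsor stating which is intended;
2. each box uses only the volume names of its own regimen, so that the CTV3000 line of the ten-fraction box agrees with item 2b;
3. the PET threshold is written the same way throughout, since 7.1 and the ten-fraction box have > 2.0 while 7.1.9 and the five-fraction box have ≥ 2.0.

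The cost is a correction to a few lines of text and two boxes, plus a notice to planners at both sites. The sample size, endpoints and analysis do not change. If patients have already been planned, the sponsor can compare the recorded combined volume with the regimen given for each one, which would settle whether the ambiguity had any effect.

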#### Five Fraction Regimen ( $\leq 65\text{cc}$ )

$\text{CTV3500\_PET} = \text{PET T/N} \geq 2.0$   
 $\text{CTV3000\_MR} = \text{Boolean}(\text{T1\_Gad} + \text{T1\_Cavity})$   
 $\text{Boolean CTV3500\_PET} - \text{CTV3000\_MR} \leq 65\text{cc}$   
 $\text{CTV2500} = (\text{Boolean CTV3500\_PET} + \text{CTV3000\_MR}) + 1\text{cm}$

Optimization Target Volume (OTV)  $\geq 2\text{mm} + \text{CTV2500}$

#### Ten Fraction Regimen ( $> 65\text{cc}$ )

$\text{CTV4000\_PET} = \text{PET T/N} > 2.0$   
 $\text{CTV3500\_MR} = \text{Boolean}(\text{T1\_Gad} + \text{T1\_Cavity})$   
 $\text{Boolean CTV4000\_PET} - \text{CTV3500\_MR} > 65\text{cc}$   
 $\text{CTV3000} = (\text{Boolean CTV3500\_PET} + \text{CTV3000\_MR}) + 1\text{cm}$

Optimization Target Volume (OTV)  $\geq 2\text{mm} + \text{CTV3000}$

\*Need to make sure all CTVs are inside the brain tissue contour

\*Need to evaluate inclusion or exclusion of small CTV volumes at a considerable distance from bulk CTV volumes

### 7.1.10 Image Guidance

The Hitachi Patient Image Alignment System (PIAS) (2D) and/or CT on rails (3D) will be used for image guidance. Both are allowed under this protocol.

### 7.1.11 Treatment Planning

- i. The prescription isodose line definition is up to the treating physician. However, we recommend that in the worst-case scenario the CTV D95% is at least 95% of the prescription dose.
- ii. The optimization method can be either multi-field optimization (MFO) or single-field optimization (SFO) also known as single-field uniform dose (SFUD). SFO optimizes the spots of each proton field individually and creates a more uniform dose distribution from each beam than MFO. MFO is usually referred to as intensity-modulated proton therapy (IMPT). In MFO, spots from all the proton fields are optimized together. The inhomogeneous dose from each field is summed up to create homogeneous target coverage.
- iii. Beam angles will be selected to spare normal tissues and improve plan robustness.
- iv. If possible patients will be planned using SFO technique. If SFO cannot meet the dose volume constraints and plan robustness requirement, robustly optimized MFO will be used.
- v. Robustness quantification to evaluate the impact of patient setup and proton beam range uncertainties will be performed. The inter-fractional setup uncertainty is assumed to be a minimum of 2 mm and proton beam range uncertainty is assumed to be a minimum of 2%. For all patients, the plan robustness will be reviewed by a physicist co-chair. We recommend that in the worst-case scenario the CTV D95% is at least 95% of the prescription dose
- vi. Linear energy transfer (LET) distribution, which is calculated by an in-house developed system, will be reviewed by a physics co-chair to make sure that no high LET spots exist in the critical organs like optic chiasm and brainstem. Otherwise a new plan would be generated at the discretion of the physicist. Alternatively biologic dose distributions may be evaluated based on the RBE model developed at Mayo Clinic in Rochester and critical organs may be protected from excessive biologic dose. A new plan may be generated at the discretion of the physicist.
- vii. Calculated dose distributions will be verified by comparison to a Monte Carlo/semi-analytic calculation. In cases where the CTV mean dose differs by more than 3% a new plan would be generated at the discretion of the physician.
- viii. The radiobiological effects evaluation is performed based on the standard of each institution. Linear energy transfer (LET) distribution and/or biologic dose will be reviewed by the clinical team (radiation oncologist, dosimetrist, and physicist). Plans may be modified, within the protocol-specified dose-constraints, as per standard clinical practice to minimize high LET spots and/or biologically enhanced dose in the critical organs like optic chiasm and brainstem.

### 7.1.12 Treatment Delivery

The corresponding treatment delivery techniques as employed in the treatment planning will be used to deliver the plan.

### Prescription Deviations and Goals

	Goal	Min deviation (2)	Major deviation (1)
CTV	D95% = 95%	D95% = 85% - 120%	<85% or >120%

- Prescription Dose: we recommend that in the worst-case scenario the CTV D95% is at least 95% of the prescription dose and the CTV D5% is at most 120% of the prescription dose.
- Minor deviation: CTV D95%: 85-95% of the prescription dose, CTV D5%: 110-120% of the prescription dose in the worst-case scenario.
- Major deviation: CTV 95% : <85% of the prescription dose, CTV D5%: >120% of the prescription dose in the worst-case scenario.
- Volume: The CTV must be specified on any plans with dose –volume histograms for these and all critical organs
- Critical structures in Table 7.1 with the dose volume indices up to 110% of the limit will be considered a minor deviation. Critical structures in Table 7.1 with the dose volume indices more than 120% of the limit will be considered a major deviation.

#### 7.1.13 Critical Structures

Table 7.1 Dose volume constraints for critical structures in the nominal scenario. Minor deviation (110% of the limit) is allowed in the worst-case scenario

FIVE FRACTION	Volume	Volume Max Gy[RBE]	Max Point Dose Gy[RBE]
Optic Pathway	<0.2 cc	23 Gy[RBE]	25 Gy[RBE]
Brainstem	<0.5 cc	23 Gy[RBE]	31 Gy[RBE]
Skin	<10 cc	36.5 Gy[RBE]	38 Gy[RBE]

TEN FRACTION	Volume	Volume Max	Max Point Dose
Optic Pathway	<0.5cc	32 Gy[RBE]	37.5 Gy[RBE]
Brainstem	<0.5 cc	33 Gy[RBE]	40 Gy[RBE]
Skin	<10 cc	43.2 Gy[RBE]	45.6 Gy[RBE]

#### 7.1.14 Quality Assurance Documentation

All plans will be reviewed by the PI and/or the co-PIs and rated as within guidelines (no deviations), minor deviation (any number of minor deviations mentioned above), or major deviation (1 or more major deviations present)

## 7.2 Patient Outcomes Quality of Life Assessment [Database]

7.2.1 The EORTC QLQ-C30 and QLQ-BN20 will be completed, and a MMSE will be performed per the scheduled test timepoints.

### **7.3 Adjuvant therapy**

Patients will receive concurrent chemotherapy, temozolomide (75 mg/m^2 daily, d1-7 (5 day RT regimen) or d1-14(10 day RT regimen) during radiation followed by 6 cycles of temozolomide (150-200 mg/m^2) starting one month post radiation (d1-5 cycle q 28 days). This will be given and administered in standard doses as per institutional and standard regimen guidelines. Dose modifications will be done as per standard institutional guidelines. Alternating electric field therapy will be allowed during the adjuvant temozolomide phase of treatment.

### **7.4 Follow-up protocol**

Post-treatment tumor recurrence will be monitored through follow-up imaging, using standard of care MRI (including pMRI and DTI sequences) per protocol and then when recommended by treating physician during the event monitoring phase to assess tumor response based on the Response Assessment in Neuro-Oncology (RANO) Working Group criteria until progression of disease (up to 5 years). Central review will be required to verify progression ([name], neuroradiology to review).

### **7.5 Patterns of Failure**

For those who recur, follow-up imaging at progression will be co-registered with pre-treatment imaging in the Eclipse treatment planning software (Varian Medical Systems, Palo Alto, CA), and patterns of failure will be analyzed by determining the portion of the recurrence volume (RecVol) that falls within the delivered RT plan and classifying each recurrence as either 'central' (>95% isodose line(IDL)), 'in field' (80 - 95% IDL), 'marginal' (20 - <80% IDL), or 'distant' (<20% IDL).

### **7.6 Outcomes**

Outcomes for patients treated prospectively with the addition of F-DOPA-PET will be determined and compared against historical controls from patients treated on NCCTG clinical trials.

### **7.7 Quality of life – patient reported outcomes**

QOLs will be compared to high-grade glioma patients treated on Keime-Guibert et al. that examined a similar group. QOL and cognitive function will be evaluated with the EORTC QLQ-C30 and QLQ-BN20 and Mini-Mental Status Exam (MMSE) questionnaires. Every patient will be asked to complete the whole form packet at baseline and at each MRI evaluation for a maximum of 6 evaluations. These time points are selected to capture the quality of life profile and correlate findings with radiologic and clinical progression as well as time points used on prior studies to allow historical comparisons.

## **8.0 Dosage Modification Based on Adverse Events**

If a patient develops an allergic reaction during injection of F-DOPA, the patient is not to receive any additional tracer and will not undergo PET imaging and will go off study.

## **9.0 Ancillary Treatment/Supportive Care: none**

## **10.0 Adverse Event (AE) Monitoring and Reporting**

### **10.1 Adverse Event Characteristics**

**CTCAE term (AE description) and grade:** The descriptions and grading scales found in the revised NCI Common Terminology Criteria for Adverse Events (CTCAE) version 4.0 will be utilized for AE reporting. All appropriate treatment areas should have access to a copy of the CTCAE version 4.0. A copy of the CTCAE version 4.0 can be downloaded from the CTEP web site:

[\(http://ctep.cancer.gov/protocolDevelopment/electronic\\_applications/ctc.htm\)](http://ctep.cancer.gov/protocolDevelopment/electronic_applications/ctc.htm)

- a. Identify the grade and severity of the event using the CTCAE version 4.0.
- b. Determine whether the event is expected or unexpected (see Section 10.2).
- c. Determine if the adverse event is related to the study intervention (agent, treatment or procedure) (see Section 10.3).
- d. Determine whether the event must be reported as an expedited report. If yes, determine the timeframe/mechanism (see Section 10.4).
- e. Determine if other reporting is required (see Section 10.5).
- f. Note: All AEs reported via expedited mechanisms must also be reported via the routine data reporting mechanisms defined by the protocol (see Sections 10.6 and 18.0).

**NOTE:** A severe AE is NOT the same as a serious AE, which is defined in Section 10.4.

### **10.2 Expected vs. Unexpected Events**

*Expected events* are those described within the study specific consent form, package insert (if applicable), and/or the investigator brochure, (if an investigator brochure is not required, otherwise described in the general investigational plan).

*Unexpected adverse events* or suspected adverse reactions are those not listed in Section 15.0 of the protocol, the study specific consent form, package insert (if applicable), or in the investigator brochure (or are not listed at the specificity or severity that has been observed); if an investigator brochure is not required or available, is not consistent with the risk information described in the general investigational plan.

*Unexpected* also refers to adverse events or suspected adverse reactions that are mentioned in the investigator brochure as occurring with a class of drugs but have not been observed with the drug under investigation.

An investigational agent/intervention might exacerbate the expected AEs associated with a commercial agent. Therefore, if an expected AE (for the commercial agent) occurs with a higher degree of severity or specificity, expedited reporting is required.

**NOTE:** *The consent form may contain study specific information at the discretion of the Principal Investigator; it is possible that this information may NOT be included in the protocol or the investigator brochure. Refer to protocol or IB for reporting needs.*

### **10.3 Attribution to agent(s) or procedure**

Patients will be observed for adverse events for approximately 15-20 minutes post  $^{18}\text{F}$ -DOPA injection by the Nuclear Medicine health professionals administering the scan.

Patients will be regularly evaluated by a radiation oncology health professional per standard clinical practice throughout their course of external beam radiation therapy.

When assessing whether an adverse event is related to a medical treatment or procedure, the following attribution categories are utilized:

Definite - The adverse event *is clearly related* to PET scanning and  $^{18}\text{F}$ -DOPA injection

Probable - The adverse event *is likely related* to PET scanning and  $^{18}\text{F}$ -DOPA injection

Possible - The adverse event *may be related* to PET scanning and  $^{18}\text{F}$ -DOPA injection

Unlikely - The adverse event *is doubtfully related* to PET scanning and  $^{18}\text{F}$ -DOPA A injection

Unrelated - The adverse event *is clearly NOT related* to PET scanning and  $^{18}\text{F}$ -DOPA injection

Definite - The adverse event *is clearly related* to hypofractionated proton beam therapy.

Probable - The adverse event *is likely related* to hypofractionated proton beam therapy.

Possible - The adverse event *may be related* to hypofractionated proton beam therapy.

Unlikely - The adverse event *is doubtfully related* to hypofractionated proton beam therapy.

Unrelated - The adverse event *is clearly NOT related* to hypofractionated proton beam therapy.

**Events determined to be possibly, probably or definitely attributed to a medical treatment suggest there is evidence to indicate a causal relationship between the drug/treatment and the adverse event.**

